9.7.1.3 Number of cases to effectiveness assessment

These cases include those who signed the data release consent form to participate in this study, visited as per the study schedule, took Spesolimab IV, and were evaluated for the effectiveness.

Based on the MFDS guideline, the cases below shall be excluded from effectiveness analysis (defined below):

- a. Patients excluded from the safety analysis set listed in section [9.7.1.3](#).
- b. Patients missing information of effectiveness assessment listed in section [9.3.2.2](#).

9.7.2 Safety analysis

Safety analyses will be performed on the safety set.

Frequency of safety events will be reported using numbers of patients with AEs, frequencies, incidence with 95% CIs. AEs will be tabulated by system organ class and preferred term for overall and for subgroup based on demographics and baseline characteristics.

Categorical variables will be reported using numbers of patients with AEs, frequencies, incidence with 95% CIs. Incidence will be analyzed using Pearson's chi-square or Fisher's exact test to determine if there are statistically significant differences.

Continuous variables will be reported using number of patients. Incidence will be reported using odds ratios and 95% CIs by simple logistic regression.

As a result of simple logistic regression, statistically significant variables will be reported using odds ratios and 95% CIs by multiple logistic regression.

AEs will be coded with the current version of the Medical Dictionary for Regulatory Activities (MedDRA). Past / concomitant therapies will be coded according to the current version of the Anatomical Therapeutic Chemical (ATC) classification system.

Safety analyses will be based on all patients treated, i.e. all patients who received at least one dose of Spesolimab IV. However, if data for patients who have been treated with Spesolimab IV beyond the scope of approved label are collected, these will be listed separately.

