9.3.2 Outcomes

9.3.2.1 Primary outcomes

The primary outcomes are the safety outcomes until study completion, calculated as the incidence of:

- Adverse events (AEs)
- Adverse drug reactions (ADRs)
- Serious adverse events (SAEs)
- Serious adverse drug reactions (SADRs)
- Unexpected adverse drug reactions
- Adverse events of special interest (AESIs)
- Adverse events leading to temporary or permanent discontinuation
- Adverse events leading to death

Assessment of safety:

- AE (event name / symptom / sign)
- Onset date and end date
- Intensity (mild / moderate / severe)
- Seriousness (serious / non-serious)
- Outcome of the event (recovered / not yet recovered / sequela / fatal / unknown)
- Causality (certain / probable-likely / possible / unlikely / conditional-unclassified / unassessable-unclassifiable)
- Action taken with study drug due to AE (dose not changed / dose reduced / dose increased / drug withdrawn / not applicable)
- AESIs (systemic hypersensitivity reactions including infusion reactions and anaphylactic reaction / severe infections / opportunistic and mycobacterium tuberculosis infections)

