9.5 STUDY SIZE

The enrolment target is 21 patients for a total of 6 years, considering the prevalence of generalized pustular psoriasis with acute flares in Korea and the market conditions. [REDACTED] is committed to collecting data from all patients who receive Spesolimab IV within a 2-year period after the product's launch (complete enumeration).

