9.7.3 Effectiveness analysis

Effectiveness analysis will be performed on the effectiveness set.

Effectiveness analyses will be performed by subgroup based on demographics and baseline characteristics.

The standard descriptive statistical parameters (number of patients, mean, standard deviation, median, minimum, maximum, etc.) will be summarized.

The changes of the effectiveness outcomes from baseline will be compared in an exploratory sense via paired t-test.

For investigator's overall effectiveness evaluation, the number and percentage of patients will be presented. If the result of overall evaluation is 'improved', it will be classified as 'effective'. If the result of overall evaluation is 'unchanged' or 'aggravated', it will be classified as 'ineffective'.

'Effective' and 'ineffective' will be reported using numbers of patients, percentages with 95% CIs.

Categorical variable will be reported using numbers of patients, numbers of patients assessed as 'effective', effective rates and 95% CIs. Effectiveness will be analyzed by Pearson's chi-square test or Fisher's exact test to determine if there are statistically significant differences.

Continuous variable will be reported using numbers of patients. Odds ratio and 95% CIs by simple logistic regression will be summarized.

To estimate any factors that are thought to influence an effective rate, logistic regression analysis and/or poisson regression will be conducted, and for statistically significant covariates the meaning will be described.

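### Logistic regression is set for adverse event incidence and for the effective rate with a target of 21 patients and no provision for sparse outcomes; a penalised or exact method with a minimum-count rule would serve better

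*Protocol*

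**What the plan says.** Protocol section 9.5 states: "The enrolment target is 21 patients for a total of 6 years". The reason given is "considering the prevalence of generalized pustular psoriasis with acute flares in Korea and the market conditions"; no event rate, effect size, power or precision enters.

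Section 9.3.2.1 introduces eight outcomes with "The primary outcomes are the safety outcomes until study completion, calculated as the incidence of". They run from all adverse events to serious adverse drug reactions, events of special interest and fatal events.

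Section 9.7.2 first promises counts and incidence with 95% confidence intervals. It sends categorical variables to a chi-square or Fisher's exact test. For the rest it says "Continuous variables will be reported using number of patients", followed by "Incidence will be reported using odds ratios and 95% CIs by simple logistic regression". It then adds that "statistically significant variables will be reported using odds ratios and 95% CIs by multiple logistic regression".

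Section 9.7.3 follows the same pattern for the effective rate. Categorical variables get a chi-square or Fisher's exact test, and for continuous variables "Odds ratio and 95% CIs by simple logistic regression will be summarized". A later sentence on factors that influence the effective rate allows logistic regression, Poisson regression or both.

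The abstract calls all analyses exploratory, and section 9.7 leaves full details to the SAP.

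**The concern.** Fisher's exact test is offered for categorical variables, so small counts were foreseen there. Nothing comparable is said for the regressions. Unqualified logistic regression is normally run as maximum likelihood, which behaves poorly with 21 patients and few events, or few non-events if nearly all patients respond.

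Three things can go wrong:

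- With no events, there is no odds ratio.
- If a factor separates patients with and without the event, the estimate is infinite, and software prints an arbitrary number with meaningless Wald limits.
- Otherwise the estimate is unstable and on average too far from 1.

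Choosing variables by significance before the multiple model favours the most exaggerated estimates. The results go to the Korean regulator and, by section 7, are reflected in the approved information. An inflated odds ratio from a handful of events could there be misread as a risk factor.

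**Working it through.** **Inputs.** n = 21 (section 9.5). The models are those of sections 9.7.2 and 9.7.3, read as standard maximum likelihood. The protocol states no event rates, so a range is assumed. The study size has no statistical inputs, so there is no figure of the plan's own to reproduce.

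**1. How many events to expect.** P(0 events) = (1 − p)^21. P(at most 3) is the sum of C(21,k) p^k (1 − p)^(21−k) for k = 0 to 3.

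| True rate p | P(0 events) | P(at most 3 events) |
|---|---|---|
| 2% | 65% | 99.9% |
| 5% | 34% | 98% |
| 10% | 11% | 85% |
| 15% | 3% | 61% |
| 20% | 1% | 37% |
| 30% | 0.1% | 9% |

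By symmetry, the chance of at most 3 patients rated ineffective is 37% at an effective rate of 80%, 85% at 90% and 98% at 95%.

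**2. How often the estimate is infinite, with no true association.**

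- One continuous factor, k events: 2/C(21,k). This is 2/21 = 9.5% for one event, 2/210 = 1.0% for two and 2/1330 = 0.15% for three.
- Several continuous factors, two events, by simulation: about 5% with two factors and 19% with three.
- A binary factor splitting patients 10/11, two events: [C(10,2) + C(11,2)]/C(21,2) = (45 + 55)/210 = 48%. Split 3/18: (3 + 153)/210 = 74%.

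The simple models in both sections are attached to continuous variables, so the first line applies to them. The binary figures apply only if such factors enter the multiple model or the effective-rate factor analysis. Poisson regression is no escape there, because a zero cell also gives an infinite ratio.

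**3. Bias and instability when the estimate is finite.** Simulation with n = 21, one standard normal covariate and a true odds ratio of 2 per standard deviation.

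- Maximum likelihood, unseparated data, event rates 5% to 90%: geometric-mean odds ratio 2.29 to 2.76, median 1.99 to 2.22. At a 50% event rate the geometric mean is still 2.38, so part of the bias comes from n = 21 itself.
- At base incidences of 10% to 30%, 5% to 10% of maximum-likelihood fits show an odds ratio of 10 or more, against 2% to 4% for Firth.
- Firth, all data sets with at least one event and one non-event: geometric mean 1.91 to 2.04. Restricted to unseparated data, its geometric mean is about 1.8 to 2.0 and its median about 1.7 to 1.9.
- The root mean squared error of the log odds ratio is 27% to 36% lower with Firth in one set of simulations and about 40% to 58% lower in another. In the latter it stays about 40% to 53% lower after outcomes with fewer than 3 events or non-events are dropped.

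**4. Effect of the significance screen.** The protocol gives no threshold; Wald p < 0.05 is assumed. Among unseparated fits that pass, the median maximum-likelihood odds ratio is 8.1, 6.6 and 5.9 at base incidences of 10%, 20% and 30%, for a true value of 2. Firth on the same data sets gives 4.9, 4.5 and 4.2, which reduces the exaggeration but does not remove it.

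**5. What remains with no events.** For 0/21 the exact 95% interval for the incidence is 0% to 1 − 0.025^(1/21) = 16.1%.

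**The case against.** The strongest reply is that the protocol does not fix the estimator. It never mentions maximum likelihood. Firth and exact logistic regression are both logistic regression with an odds ratio and interval, so an SAP could name either without contradicting the text. That stands, and it limits the weight of the point. But the protocol states the model as firm text, and its default reading is maximum likelihood.

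A reader might infer that regression is prescribed for every safety outcome, including serious reactions and deaths. The documents do not say so. Section 9.7.2 writes of incidence without limiting it, and section 9.3.2.1 defines eight outcomes as incidences, but no sentence joins the two. Incidence of adverse events in general is an equally natural reading. Nor do the documents show that many outcomes will have three events or fewer. That is plausible for deaths, serious reactions and events of special interest, and unproven for all adverse events.

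A reader might also infer that infinite odds ratios will be common. For one continuous factor with two or more events they are not. Categorical factors go to a chi-square or Fisher's exact test, and Fisher's test copes with zero cells.

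Finally, the median estimate is nearly right. With no true association, fewer than 2% of data sets are Wald-significant. With one to three events the figure is below 1% even at a true odds ratio of 2, so the screen would seldom send anything forward in the sparsest case. Exaggeration and instability are the problem, not a flood of false signals. The counts and incidences with intervals, which are the main description of rare events, are unaffected.

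**Conclusion.** The concern holds in a limited form. For continuous variables the protocol sets simple logistic regression for incidence, followed by a multiple model on significant variables, and simple logistic regression for the effective rate. With 21 patients it makes no provision for sparse data.

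The conclusion rests on two assumptions: standard maximum likelihood, and outcome rates of about 15% or less (or an effective rate high enough to leave few failures). Estimates are then often unavailable or unstable, and biased away from 1 on average though little in the median. Those that pass a significance screen are exaggerated to about 6 to 8 for a true value of 2.

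The protocol does not support the stronger claims that logistic regression is the only model for the effective rate, or that zero-cell rates of 48% to 74% apply to the simple models. Because the analyses are exploratory and the SAP may already address this, it is a modest improvement worth making because it is cheap.

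**What to change.** In sections 9.7.2 and 9.7.3, specify Firth-penalised logistic regression with profile-likelihood 95% confidence intervals, or exact logistic regression, for both the simple and the multiple models.

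Add one rule: where too few patients have, or lack, the outcome, report only counts, case listings and the incidence with an exact confidence interval, and no odds ratio. Fewer than 3 would be a workable limit, but it is a conventional choice and not a derived one. If the SAP already contains such provisions, a cross-reference is enough.

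The cost is a sentence or two in each section and a standard software option; design, data collection and study size are unchanged. The price is slight shrinkage (Firth median about 1.7 to 1.9 for a true odds ratio of 2) and no odds ratio for the rarest outcomes. Firth does not cure selection by significance, so screened estimates still need cautious wording.

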Variables:	
Outcomes of safety:
 
All reported adverse event (AE)s in patients who take at least one dose of Spesolimab IV
 
Outcomes of effectiveness:
 
Changes in the Generalized Pustular Psoriasis Physician Global Assessment (GPPGA) pustulation sub-score (mandatory), GPPGA score (mandatory), Psoriasis Area and Severity Index for Generalized Pustular Psoriasis (GPPASI) (if collected), pain Visual Analog Scale (VAS) (if collected) and Psoriasis Symptom Scale (PSS) (if collected) from baseline after 1 week and/or 4 weeks

Data sources:	Patients' medical records
Study size:	21 patients
Data analysis:	All statistical analyses will be explorative in nature. Patient characteristics will be reported using measures of central tendency (e.g., mean, median) and variance (standard deviation, quartiles) for continuous variables and using frequencies and percentages for count data. Frequency of safety events will be reported using frequencies and incidence with 95% confidence interval (CI). The changes of the effectiveness outcomes from baseline will be compared in an exploratory sense via paired t-test.
Milestones:	
Start of data collection: March 2025
 
End of data collection: August 2029
 
Final study report: November 2029

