9.3.3 Covariates

- 1) Patient characteristics
 - Demographics: age, gender, current pregnancy status, current breastfeeding status, smoking status, alcohol intake status
 - Physical examination: height, weight, blood pressure, body temperature, pulse rate
 - Disease information: duration of disease, IL-36RN mutation status, medical history, past / concomitant medications or therapies, history and frequency of GPP flares, comorbidities (CV, hepatic or renal impairments, infection, skin diseases (i.e., plaque psoriasis)), family history
- 2) Spesolimab IV administration status: total duration of administration, total administered dose, average daily dose
- 3) Subsequent exposure to subcutaneous Spesolimab: total duration of administration, total administered dose
- 4) Patients of special investigation: pediatric population, geriatric population, pregnant women, lactating women, hepatic impairment, renal impairment
- 5) Laboratory test results
- 6) Others

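### With 21 patients, refitting the significant variables in a multiple logistic model (9.7.2) gives exaggerated odds ratios with 95% CIs that under-cover

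*Protocol*

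**What the plan says.** Section 9.5 of the protocol sets the size: "The enrolment target is 21 patients for a total of 6 years". The reasons given are prevalence and market conditions. Data are also to be collected from every patient treated in the two years after launch, but no other number is given.

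Section 9.7.2 sends categorical variables to Pearson's chi-square or Fisher's exact test. Under continuous variables it says: "Incidence will be reported using odds ratios and 95% CIs by simple logistic regression." It then adds the rule at issue: "As a result of simple logistic regression, statistically significant variables will be reported using odds ratios and 95% CIs by multiple logistic regression." It states no cap on covariates, no significance level and no rule for sparse data.

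The candidates in section 9.3.3 begin with "Demographics: age, gender, current pregnancy status, current breastfeeding status, smoking status, alcohol intake status". They continue through examination findings, disease history, comorbidities, exposure and laboratory results to an open item for others, about 20 or more in all. Section 9.3.2.1 introduces eight safety categories with "The primary outcomes are the safety outcomes until study completion, calculated as the incidence of".

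For effectiveness, section 9.7.3 says that "logistic regression analysis and/or poisson regression will be conducted, and for statistically significant covariates the meaning will be described". The abstract says: "All statistical analyses will be explorative in nature."

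**The concern.** The rule chooses variables because they look significant and then reports odds ratios and 95% CIs for those variables from the same patients, as if they had been named beforehand. An estimate that must pass a significance threshold to be reported is, on average, too far from 1, and its interval no longer covers at the stated rate. With so few patients the threshold is passed only by extreme estimates, so the exaggeration is large. Sparse tables can also separate the outcome completely, and then the maximum-likelihood odds ratio does not exist.

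At stake is a post-marketing report to the Korean regulator that names factors for adverse events with odds ratios and intervals that do not mean what they say.

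**Working it through.** **Inputs.** From the protocol: n = 21 (9.5) and the screen-then-refit rule (9.7.2). Not given, so assumed: two-sided 5% level (taken from the 95% CIs); outcome rate 30–80%; covariate set of either 9 continuous variables (the narrow reading of 9.7.2) or 15 mixed continuous and binary ones; screening by likelihood-ratio or Wald test. There is no planned figure to reproduce.

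**1. Information available.** Whatever the event rate, the smaller outcome class holds at most floor(21/2) = 10 patients. Per candidate that is at most 10/9 = 1.1, 10/15 = 0.67 or 10/20 = 0.5.

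**2. Benchmark for false selection.** For k independent tests at an exact 5% level, P(at least one) = 1 − 0.95^k: 37% for k = 9, 40% for 10, 54% for 15, 64% for 20.

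**3. Why the intervals fail.** Suppose one null variable passes a Wald screen. The multiple model then contains only that variable, so it is the same fit, and its 95% CI excludes 1 because that is how it was chosen. Coverage in that case is zero. It rises above zero overall only because two or more variables are sometimes selected and an adjusted interval can include 1 again. With a likelihood-ratio screen, the test and the Wald interval disagree in small samples, so coverage is lost less completely.

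**4. Null simulation (n = 21, no true effect, both covariate sets, rates 30–80%).**

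| | Likelihood-ratio screen | Wald screen |
|---|---|---|
| At least one false factor selected | 43–65% of studies | 8–29% of studies |
| Coverage of the 95% CI, selected variables, converged fits | 65–88% | 13–20% |
| Selected models non-estimable | 1–52% | about 0–1% |

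The non-estimable share depends mainly on the covariate mix: binary covariates cause most of the separation.

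**5. One true predictor (odds ratio 2 per SD) among 20 covariates, rates 20–50%.**

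| | Likelihood-ratio screen | Wald screen |
|---|---|---|
| True predictor found | 29–32% | 8–18% |
| Its median estimated odds ratio when found | 4.1–5.9 | 5.5–7.8 |
| Share of selected variables that are false | 79–82% | 70–77% |

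With 10 covariates the false share falls to 65–66% (likelihood ratio) or 48–51% (Wald). With a true odds ratio of 4 per SD and 20 covariates it is 42–49% (Wald).

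**6. What depends on size.** At n = 200 (rate 33%, odds ratio 2, 20 covariates, likelihood ratio) no fit failed and the median odds ratio of the true predictor was 2.0. Non-estimability and exaggeration of a true effect therefore come from the small sample. False selection does not: half of the selected variables were still false, and coverage over all selected variables was 62%. At n = 40, in case full enumeration exceeds 21, 8–10 null continuous covariates with likelihood-ratio screening still gave a false factor in 33–47% of studies, with coverage of 39–61%.

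**7. A limit of the result.** At a 10% event rate with 20 null covariates and likelihood-ratio screening, coverage was close to nominal (about 95%), but about 70% of the refits failed. With Wald screening at that rate, nothing was selected in about 97% of runs.

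**8. Poisson option in 9.7.3.** If a binary outcome is fitted with the model-based Poisson variance, p replaces p(1 − p), so standard errors are too large by 1/√(1 − p): 1/√0.3 = 1.83 at 70% effective and 1/√0.2 = 2.24 at 80%.

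**The case against.** The strongest reply has four parts.

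- **Everything is declared exploratory, and the analysis plan may add detail.** True, and this lowers the consequence. But 9.7.2 already fixes the selection rule, and the exploratory label does not restore the coverage of a reported 95% CI.
- **The text does not screen every covariate by logistic regression.** This stands. Categorical variables go to chi-square or Fisher's test, and simple logistic regression is stated under continuous variables. A reader might infer that all of 9.3.3 enters the screen; the wording does not say so. The 9-covariate continuous case allows for this, and the fault remains.
- **Outcomes depend on choices that the protocol does not make.** This also stands. A reader might infer that the method cannot work at 21 patients, or that most of its products will be false or non-estimable. The documents do not support that: with Wald screening the commonest null result is that nothing is selected, and almost every selected model can be fitted.
- **Poisson regression is a separate matter.** It appears only in 9.7.3, as an alternative and with no screen-then-refit step. Model-based variance is an assumption, and it would widen intervals, giving fewer false factors rather than more. It adds nothing to the case against 9.7.2.

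A reader might also infer that spurious factors will enter the approved information. The protocol says this of the surveillance results in general, and its primary outcomes are incidences, not regression factors.

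**Conclusion.** The point holds for the multiple-logistic sentence in 9.7.2. Under both readings of the covariate set and both screening tests, at outcome rates of 30–80%, the selected variables' intervals under-cover and the odds ratios are biased away from 1. How often a false factor appears (8–65% of studies) and how often the model cannot be estimated (about 0–52% of selected models) depend on the test, the event rate and the covariate mix, none of which the protocol gives. The simulations assume independent covariates and a 5% level.

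In 9.7.3 the fault is narrower: only the statistically significant covariates are to be interpreted, which is selective reporting without a stated refit. The primary incidences and their CIs are unaffected. The wording should be changed, but the aims of the study are not undermined.

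**What to change.** **Section 9.7.2.** Delete the sentence on multiple logistic regression. Name a few baseline factors recorded in all patients, for example age group and sex. For each level report n/N with an exact 95% CI, and use Fisher's exact test. The width of such intervals is plain to the reader: 7/21 is 33.3% (14.6–57.0%). Where an odds ratio is wanted, give a one-covariate exact or Firth-penalised logistic estimate for every prespecified factor, whether significant or not.

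**Section 9.7.3.** Report the same prespecified factors in the same way, instead of interpreting only the significant ones. Do not use number of infusions as a factor for effectiveness: the flow chart ties an additional dose to persisting flare symptoms, so the factor follows from non-response. IL-36RN status is collected only if available and is therefore a poor choice of main factor. If Poisson regression of the binary outcome is kept, specify robust variance.

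**Cost.** Adjusted odds ratios are lost, though at this size they would be unreliable. Programming is reduced. The wording change is a protocol amendment, and under 10.1 amendments need ethics committee and authority approval.
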